13.2 Changes from Interim Analysis SAP to Final Analysis SAP

- 1. Following the full approval of agalsidase beta, the final analysis was changed to non-inferiority.
- 2. The primary analysis was changed to the two-stage with quantile regression, and the RIRS (primary analysis for the interim analysis) is now a supportive analysis. This change was discussed and agreed with the FDA. In addition to estimating the median slope, quantile regression will be used to estimate the 25th and 75th quantiles as supportive analysis.
- 3. In the FDA interaction, the agency suggested to remove UPCR from the model. Following that, UPCR was removed from all models (RIRS, RI, 2-stage with ANCOVA, MMRM for eGFR change from BL and for lyso-Gb3 change from BL). Quantile regression for the median which includes UPCR as a covariate is used as a sensitivity analysis.
- 4. All models considered as sensitivity for the primary endpoint are conducted on the PP and ITT sets.
- 5. In the sensitivity analyses for missing data: MI under missing not at random and tipping point which are more relevant for superiority were removed.
- 6. Changes were made to Section 17: code for quantile regression was added and modifications to the MI under MAR were done in light of the change in the primary model. Removal of UPCR from the models was implemented.
- 7. Section 16 (unblinding plan) was revised due to the unplanned discussion with the FDA regarding the primary analysis.
- 8. The section on simulations to support the model was removed. Simulations were provided to the FDA.
- 9. Text with instructions related to the interim analysis removed (e.g., handling of ongoing events at the cut-off date for the interim analysis).
- 10. Criteria that injection site reactions should occur within 24 hours of infusion was added to the identification of injection site reactions. The rationale for this change is that during the review of interim TFL, several events that were classified as injection site reaction based on their SOC/PT time of occurrence was remote from the time of the infusion, which was judged by the clinicians as not injection site reactions.
- 11. Table 3 of SOC and PT to identify injection site reactions was updated.
- 12. A clarification was added to the derivation of duration of treatment with fabrazyme prior to the study.
- 13. A derivation for LVMi was added, in case LVM is available at a visit but LVMi is missing.
- 14. Listing of serious TEAE and of related TEAE were added.
- 15. At the interim analysis, IRR were considered to occur within 2 hours. For the final analysis two-time frames of IRR are considered: within 2 hours and within 24 hours.
- 16. Following analysis that was done as part of the Summary of Clinical Safety (2.7.4) for the MAA, an analysis of infusion premedication and IRR-2H was added.
- 17. In light of the 2:1 randomization ratio, adjustment to the exposure is added when presenting number of TEAE, number of IRR and number of FCE.
- 18. Adding a shift table for ADA: from baseline to visit 53.
- 19. Since randomization often occurred about two weeks prior to 1st infusion, Kaplan-Meier curves are updated to measure time from date of 1st infusion instead of randomization. In case of no events, time should be censored at the time of last infusion.

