1. INTRODUCTION

This statistical analysis plan (SAP) contains detailed information on the definition of the analysis populations, derivation of variables, conventions of analysis scope, and statistical methodology for the analyses of efficacy and safety of pegunigalsidase alfa (also known as PRX-102) and agalsidase beta administered by intravenous (IV) infusion based on data collected per protocol PB-102-F20, a Phase 3 study sponsored by Protalix Ltd. Should the SAP and the protocol be inconsistent with respect to the planned analyses, the language of the SAP is governing.

The pharmacokinetic (PK) analysis is not within the scope of this SAP and is detailed in a standalone PK analysis plan.

A pre-planned interim analysis occurred when the last patient completed the 12-month visit to support a Marketing Authorization Application (MAA) submission to the European Medicines Agency (EMA). The final analysis will occur when the last patient completes the 24-month visit and will support a biologics license application (BLA) re-submission to the FDA.

The SAP that was signed on April 15th, 2021 prior to Data Base Lock (DBL) and unblinding for the interim analysis, included non-inferiority of PRX-102 compared to agalsidase beta for the interim analysis and superiority of PRX-102 compared to agalsidase beta for the final analysis. However, following the conversion of agalsidase beta to a full approval in March 2021, it was agreed with the FDA (End-of-Review Meeting, Sep 9th, 2021) that it is not necessary anymore to demonstrate superiority over agalsidase beta. A Type C meeting to reach agreement with the FDA on the proposed primary model to assess non-inferiority took place in January 21, 2022 and the SAP reflects this discussion.

In addition, analysis that were conducted as post-hoc after the interim analysis are added to the SAP, as well as some other minor changes (all are documented). None of the analyses performed at the interim analysis will be removed but following a comment by FDA, covariates were changed.

As this SAP is now only for the final analysis, sections/paragraphs relating to the interim analysis were deleted and/or updated to include only the final analysis.

In light of the unplanned conversion of agalsidase beta to a full approval and the change in regulatory requirements following that, some changes had to be made also to the unblinding plan.

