11.2 Adverse Events

Adverse events (AE) will be coded by the Medical Dictionary for Drug Regulatory Activities (MedDRA) version 19.00 or higher.

Pre-treatment AEs include all AEs occurred prior to the first study drug infusion. Pre-treatment AE will only be presented in listings.

A Treatment-emergent AE (TEAE) is defined as any AE that started post–first infusion. In case that date of onset is completely unknown, the AE will be classified as TEAE. In case the date is partially known, it will be classified as TEAE unless there is evidence, from the partial info (e.g., month of AE onset is earlier than the month of first infusion), that the AE was pre-treatment.

The number and percentage of patients with at least one TEAE and the number of TEAE will be reported by treatment arm and overall for the following parameters: Any TEAE; Related (showing jointly possibly, probably or definitely related events) TEAE; Mild or moderate TEAE; Related mild or moderate TEAE; Severe TEAE; Related severe TEAE; Serious AEs; Non- Serious AEs; Related serious AE; TEAE leading to withdrawal; Related TEAE leading to withdrawal; TEAE leading to death; and Treatment related TEAE leading to death. For selected summary tables, the

number of events will be shown together with the rate per 100 person-years defined as number of events X 100 / total exposure (in years).

In the analysis of severity, patients with event classified as "Very Severe" per CTCAE severity in eCRF will be presented in the category "Severe" for analysis.

This analysis will be repeated for the following sub-groups: ADA status, gender, FD classification and region.

The overall analysis will be repeated for injection site reaction TEAEs. Injection site reactions will be identified by their SOC and PT, as defined in Table 3 and their start time that should occur within 24 hours from the infusion, following the algorithm described in Section 11.2.3.

TEAE summary tables by the MedDRA SOC and PT will present the number and percentage of patients with at least one TEAE and the number of TEAEs. These tables will be presented by treatment arm; by treatment arm and severity; and by treatment arm and relationship to study drug.

A similar table by SOC and PT will be generated for serious TEAEs by treatment group and overall and by relationship to study drug.

In summary tables by SOC and PT, SOC will be sorted alphabetically. Within SOC, PT will be sorted in a decreasing order of PRX-102 frequency.

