11.2.1 Infusion Related Reactions (IRR)

IRRs are those TEAEs which occur during the infusion or shortly after the completion of the infusion and their causality is assessed as definitely, probably, or possibly related.

Injection site reactions with SOC and PT listed in Table 3 are not considered IRR and should not be considered for the IRR analysis.

Two time-frames will be considered for the IRR analysis: during the infusions or within 2 hours after its completion (IRR-2H) or within 24 hours after its completion (IRR-24H). Classification rules for assignment of TEAEs to occur within the time frame are provided below. All IRR tables will be done on IRR-2H. Selected tables will be repeated for IRR-24H, as described below.

Table 3: Injection Site Reaction SOC and PT

MedDRA SOC	MedDRA Preferred Term
General disorders and administration site	Infusion site discomfort
conditions	Injection site discomfort
	Infusion site pain
	Injection site pain
	Infusion site hematoma
	Injection site hematoma
	Injection site extravasation
	Infusion site extravasation
Injury poisoning and procedural complications	Contusion
	Procedural site reaction
	Procedural pain
Vascular disorders	Vein rupture
	Poor venous access

The number and percentage of patients with at least one IRR and the number of IRRs will be reported by treatment group and overall, in an overview table with the following parameters: Any IRR; Mild or moderate IRR; Severe IRR; Serious IRR; IRR leading to withdrawal; IRR leading to death. For selected summary tables, the number of IRR will be shown together with the rate per 100 infusions defined as number of IRR X 100 / Number of Infusions.

This analysis will be repeated for IRR-24H.

This analysis will be repeated for the following sub-groups: ADA status, gender, FD classification and region.

The analysis will be also by the location of administration (Home or Site), and repeated for IRR-24H.

IRR summary tables by SOC and PT will present the number and percentage of patients with at least one IRR and the number of IRRs. The tables for the IRRs will be presented overall, by severity and by seriousness. The tables by SOC and PT will be repeated for IRR-24H.

In summary tables by SOC and PT, SOC will be sorted alphabetically. Within SOC, PT will be sorted in a decreasing order of PRX-102 frequency.

IRR-2H and IRR-24H will be listed.

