16.3.1 Maintaining the Blind Due to Update of the SAP

Following the conversion of agalsidase beta to a full approval in March 2021, it was agreed with the FDA (End of Review Meeting; Sep 9, 2021) that it is not necessary anymore to demonstrate superiority over agalsidase beta for the final analysis, and that a discussion on the margin and primary analysis will take place in a subsequent Type C meeting with the FDA. It was agreed with the FDA that unblinded personnel will participate in this meeting. The Interim Analysis Team is involved in the meetings to support the proposed primary analysis and margin.

The following approach is taken with regard to updates to the SAP and TFL shells in order to maintain firewalls:

- 1. The unblinded Interim Analysis Team is responsible for preparations of material to support discussion with FDA. This also includes simulations studies and considering analytical methods discussed in recent publications.
- 2. The unblinded statistician is responsible to update the SAP and TFL shells. Changes between the two versions of the SAP will be documented in the final SAP. Two stages of SAP updates are planned in order to be able and advance with programming:
 - Stage 1: changes to safety and secondary efficacy endpoints following review of interim analysis TFL. No analyses performed at the interim analysis will be removed. The changes include:
 - Adding to the SAP, analyses that were done as post-hoc (e.g., IRR in 24-hour time frame).
 - Upon review of 1st draft of TFL, several changes to the SAS programs were done. These changes were documented in Note-To-File. Those changes are added to the final analysis SAP and are documented in Section 13.2.
 - Updates to footnotes of TFL.
 - Stage 2: changes to the primary analysis and sensitivity analysis, following agreement with FDA. No information on the simulations or any other unblinding information is to be included in the revised SAP.
- 3. The updated SAP and TFL shells will be reviewed by the unblinded Interim Analysis Team including the unblinded statistician and statistical programmer from CROS NT.

- 4. Updated SAP will be provided to the blinded team in order for the blinded statistician and programmer from CROS NT to start programming.
 - Note: stage 2 SAP and shells updates will be provided to the blinded team after meeting with the FDA.
- 5. Dry run and blinded data review meetings will be conducted by the blinded team.

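### Injection site reactions were redefined after review of the interim outputs, and no planned final output uses the definition fixed before unblinding

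*SAP*

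**What the plan says.** **The changes.** SAP 13.2 lists two changes to this endpoint since the interim SAP.

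- Item 10: "Criteria that injection site reactions should occur within 24 hours of infusion was added to the identification of injection site reactions". The reason given reads: "during the review of interim TFL, several events that were classified as injection site reaction based on their SOC/PT time of occurrence was remote" (in time, relative to the infusion). Clinicians judged that these events were not injection site reactions.
- Item 11: "Table 3 of SOC and PT to identify injection site reactions was updated". No reason is given and the earlier list is not reproduced.

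**The current definition.** SAP 11.2 identifies injection site reactions by the Table 3 terms together with "their start time that should occur within 24 hours from the infusion, following the algorithm described in Section 11.2.3". The table list in SAP 14.1 has one injection site reaction table, 14.3.3.2.

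**The link to IRR.** SAP 11.2.1 states: "Injection site reactions with SOC and PT listed in Table 3 are not considered IRR and should not be considered for the IRR analysis".

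**Who made the changes, and when.** SAP 1 dates the interim SAP to 15 April 2021, before database lock and unblinding. SAP 16.3 places anyone with access to the interim tables, listings and figures on the unblinded Interim Analysis Team. SAP 16.3.1 gives the unblinded statistician the task of updating the SAP and shells, and describes Stage 1 of that update as "changes to safety and secondary efficacy endpoints following review of interim analysis TFL".

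**The concern.** Injection site reactions and IRRs are both listed safety endpoints (SAP 2.2.4). A case definition revised by people who can see events by arm may favour one arm, even if nobody intends it and the revision is clinically sensible. The usual protection is to show the result under the definition fixed before unblinding next to the new one. The SAP does this elsewhere. The 2-hour IRR window is kept beside the new 24-hour window (SAP 13.2 item 15), and unforeseen Per Protocol violations trigger an analysis with and without the affected patients (SAP 16.3, firewall 6). It does not do so for injection site reactions, and the bias measures in SAP 16.4 do not mention safety case definitions. A reader of the final report would see one set of counts and could not tell from the planned tables how far the redefinition shaped the comparison.

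**Working it through.** No sample size, power or alpha figure is involved. The check is which counts each change can move.

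**Step 1: the two definitions.** Item 10 says the timing criterion was added, and that the events concerned had been classified by their terms. The earlier definition is therefore the earlier Table 3 with no time limit. The current one is the edited Table 3 plus the 24-hour window of SAP 11.2.3.

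**Step 2: can the 24-hour rule change IRR?** There are two ways to read the exclusion in SAP 11.2.1.

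- If exclusion is by Table 3 term, timing plays no part and IRR cannot change.
- If exclusion is by injection-site status including timing, an event that loses that status lies outside the 11.2.3 window. IRR-24H uses the same window, and the 2-hour rule in 11.2.2 is contained in it, so the event cannot enter either IRR count.

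The second reading was checked by listing every combination of Table 3 term (yes/no), related (yes/no), nine onset times (during infusion; 0.5, 1.9, 2.1, 10, 23.9, 24.1 and 72 hours after its end; incomplete), four answers to question 1 on the drug administration form (no, 1a, 1b, 1c) and linked (yes/no):

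- Combinations: 2 × 2 × 9 × 4 × 2 = 288.
- Outside the 24-hour window: 3 onset times (24.1, 72, incomplete) × 5 answer/link pairs (no, linked or not, = 2; 1a, 1b or 1c, unlinked, = 3) = 15. Over two levels of relatedness this is 30 combinations with a Table 3 term that leave the injection-site class.
- IRR-2H status changed: 0. IRR-24H status changed: 0.

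**Step 3: can the Table 3 edit change IRR?** Yes. Take the 9 × 4 × 2 = 72 combinations for a related event and add its term to Table 3:

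- Leaves IRR-2H: 3 × 8 + 6 × 2 = 36.
- Leaves IRR-24H: 6 × 8 + 3 × 3 = 57.

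Removing a term does the reverse. These are counts of logical cases, not expected event rates. Whether item 11 added, removed or only reworded terms cannot be seen.

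**Step 4: how much data had accrued.** SAP Table 5 gives, at the interim last-patient-last-visit, 48 patients at 24 months or terminated early, 13 at 18–23 months and 17 at 12–17 months. Assuming band midpoints of 20.5 and 14.5 months, and counting early terminators as complete:

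(48 × 24 + 13 × 20.5 + 17 × 14.5) / (78 × 24) = 1,665 / 1,872 = 0.889.

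With the database-lock column (60, 13 and 5 patients) the figure is 1,779 / 1,872 = 0.950. This describes exposure accrued. It says nothing about how many events moved.

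**The case against.** The strongest reply is that both changes are disclosed, that item 10 has a clinical reason applied to both arms alike, and that the outputs are descriptive, with no test or success criterion attached. All of that stands, and it keeps this a modest point.

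A second reply is that the earlier counts can be rebuilt. Table 14.3.3.3 gives all treatment-emergent events by term and arm without a time limit, and all such events are listed. This holds in part. Event counts could be summed if the earlier term list were supplied, but it is not. Patient counts cannot be added across terms without going back to the listing, and no listing of injection site reactions is planned. The interim report is only a partial substitute. It stops at the interim cut, and SAP 16.3.1 says some program changes made on review of the first draft outputs went into a note to file, so those outputs may already carry the new rule.

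Three stronger readings are tempting and are not supported:

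- A reader might infer that the 24-hour rule decides what counts as an IRR. Step 2 shows that it does not.
- A reader might set the SAP 1 statement "None of the analyses performed at the interim analysis will be removed" against item 10 and conclude that an interim analysis was dropped. Table 14.3.3.2 is still planned, so the analysis was redefined rather than removed.
- A reader might take injection site reactions to be a main expected difference between the products. Protocol 6.2 speaks of possible differences in immunogenicity and hypersensitivity, whereas Table 3 lists local and procedural events such as extravasation, contusion and poor venous access.

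**Conclusion.** The point holds in limited form. The injection site reaction definition gained a timing rule because of what was seen in the interim outputs. Its term list was edited in the same update run by unblinded staff, and no planned output uses the definition fixed before unblinding. IRR is exposed only through the Table 3 edit.

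The size and direction of any effect cannot be determined from the documents, and nothing in them shows that the changes favoured either arm. Two assumptions are involved. The interim outputs behind item 10 are taken to be the by-arm outputs that SAP 16.3 treats as unblinding. The clinicians' unblinded status is inferred from that section and is not stated in item 10. The primary analysis is unaffected. This is an inexpensive improvement to the credibility of a listed safety endpoint.

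**What to change.** Keep the new definitions as planned and add the following:

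1. Append Table 3 of the 15 April 2021 SAP to the final SAP, with a reason for each term added, removed or reworded.
2. Produce Table 14.3.3.2 by arm a second time under the earlier definition (earlier term list, no time limit), next to the planned version.
3. If any term was added or removed, also produce Table 14.3.3.8 (IRR-2H) by arm under the earlier term list. The timing rule needs no IRR re-run.
4. List each event that changes class, with its arm and onset relative to the infusion.

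Table 14.3.3.8a (IRR-24H) under the earlier list is optional. At the interim, IRR used the 2-hour window only (SAP 13.2 item 15), so there is no pre-unblinding version to restore.

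The cost is one or two extra descriptive tables, one listing and a short appendix. Programming should be light, but the note to file should be checked first to see which rule the interim programs contain.

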14. LIST OF TABLES, LISTINGS AND FIGURES

The statistical tables are to be generated using SAS version 9.4 or higher. In general, the sample size (n) is to be presented as an integer; minimum, and maximum are to be presented based on the number of decimal points of the reported value and other parameters with one more decimal point. Counts will be presented as an integer and with no decimal places. The percentage will be presented to one decimal place. The p-value will be rounded to three decimal places, unless it is less than 0.001, in which case, it will be presented as <0.001.

14.1 Tables

Number	Title	Population
14.1.1	Summary of Patients Disposition	Enrolled
14.1.2	Summary of Analysis set	Randomized
14.1.3	Summary of Critical or Major Protocol Violations	ITT
14.1.4	Summary of Patients Demographic Characteristics	ITT
14.1.4.1	Summary of Patients Demographic Characteristics by Gender	ITT
14.1.4.2	Summary of Patients Demographic Characteristics by ADA Status	ТТ
14.1.4.3	Summary of Patients Demographic Characteristics by FD Classification	ITT
14.1.4.4	Summary of Patients Demographic Characteristics by eGFR	ITT
14.1.4.5	Summary of Patients Demographic Characteristics by eGFR Slope	ITT
14.1.4.6	Summary of Patients Demographic Characteristics by Usage of ACEi or ARB	ITT
14.1.4.7	Summary of Patients Demographic Characteristics by Region (US Vs ex-US)	ITT
14.1.4.8	Summary of Patients Demographic Characteristics by UPCR Categories	ITT
14.1.5	Summary of Baseline Characteristics	ITT
14.1.5.1	Summary of Baseline Characteristics by Gender	ITT
14.1.5.2	Summary of Baseline Characteristics by ADA Status	ITT
14.1.5.3	Summary of Baseline Characteristics by FD Classification	ITT
14.1.5.4	Summary of Baseline Characteristics by eGFR	ITT
14.1.5.5	Summary of Baseline Characteristics by eGFR Slope	ITT
14.1.5.6	Summary of Baseline Characteristics by Usage of ACEi or ARB	ITT
14.1.5.7	Summary of Baseline Characteristics by Region	ITT
14.1.5.8	Summary of Baseline Characteristics by UPCR Categories	ITT
14.1.6	Summary of Fabry Disease Medical History	ITT
14.1.6.1	Summary of Fabry Disease Medical History by Gender	ITT
14.1.6.2	Summary of Fabry Disease Medical History by ADA Status	ITT
14.1.6.3	Summary of Fabry Disease Medical History by FD Classification	ITT
14.1.6.4	Summary of Fabry Disease Medical History by eGFR	ITT
14.1.6.5	Summary of Fabry Disease Medical History by eGFR Slope	ITT

14.1.6.6	Summary of Fabry Disease Medical History by Usage of ACEi or ARB	ITT
14.1.6.7	Summary of Fabry Disease Medical History by Region	ITT
14.1.6.8	Summary of Fabry Disease Medical History by UPCR Categories	ITT
14.1.7	Summary of Medical History	ITT
14.1.7.1	Summary of Medical History by Gender	ITT
14.1.7.2	Summary of Medical History by ADA Status	ITT
14.1.7.3	Summary of Medical History by FD Classification	ITT
14.1.7.4	Summary of Medical History by eGFR	ITT
14.1.7.5	Summary of Medical History by eGFR Slope	ITT
14.1.7.6	Summary of Medical History by Usage of ACEi or ARB	ITT
14.1.7.7	Summary of Medical History by Region	ITT
14.1.7.8	Summary of Medical History by UPCR Categories	ITT
14.1.8	Summary of Treatment Compliance	ITT
14.1.9	Compliance with Infusions and eGFR Assessments During COVID-19 Pandemic	ITT
14.2.1.1	Summary of eGFR	ITT
14.2.1.1.1	Summary of eGFR by Gender	ITT
14.2.1.1.2	Summary of eGFR by ADA Status	ITT
14.2.1.1.3	Summary of eGFR by FD Classification	ITT
14.2.1.1.4	Summary of eGFR by eGFR	ITT
14.2.1.1.5	Summary of eGFR by eGFR Slope	ITT
14.2.1.1.6	Summary of eGFR by Usage of ACEi or ARB	ITT
14.2.1.1.7	Summary of eGFR by Region	ITT
14.2.1.1.8	Summary of eGFR by UPCR Categories	ITT
14.2.1.2	Summary of eGFR	PP
14.2.1.3	Summary of eGFR excluded due to AKI	ITT
14.2.1.4.1	Primary Analysis: eGFR Slope Analysis Using Quantile Regression for the Median	ITT
14.2.1.4.2	Sensitivity Analysis: eGFR Slope Analysis Using Quantile Regression for the Median	PP
14.2.1.4.3	Sensitivity Analysis: eGFR Slope Analysis Using Quantile Regression for the Median Adjusting to UPCR	ITT
14.2.1.4.4	Sensitivity Analysis: eGFR Slope Analysis Using Quantile Regression for the Median Adjusting to UPCR	PP
14.2.1.5.1	Summary of eGFR Slopes (1 st Stage of 2-Stage Sensitivity Analysis)	ITT
14.2.1.5.2	Summary of eGFR Slopes (1st Stage of 2-Stage Sensitivity Analysis)	PP
14.2.1.6.1	Supportive Analysis: eGFR Slope Analysis Using Two-Stage ANCOVA	ITT
14.2.1.6.2	Supportive Analysis: eGFR Slope Analysis Using Two-Stage ANCOVA	PP

14.2.1.7.1	Supportive Analysis: eGFR Slope Analysis Using Random Intercept Model	ITT
14.2.1.7.2	Supportive Analysis: eGFR Slope Analysis Using Random Intercept Model	PP
14.2.1.7.3	Supportive Analysis: eGFR Slope Analysis Using Random Intercept Random Slope Model	ITT
14.2.1.7.4	Supportive Analysis: eGFR Slope Analysis Using Random Intercept Random Slope Model	PP
14.2.1.8	Supportive Analysis: eGFR Change from Baseline Using MMRM	ITT
14.2.1.9	Supportive Analysis: eGFR Slope Analysis Using Quantile Regression with Multiple Imputations Under MAR	ITT
14.2.1.10.1	Supportive Analysis: eGFR Slope Analysis Using Quantile Regression for the 25 th Percentile	ITT
14.2.1.10.2	Supportive Analysis: eGFR Slope Analysis Using Quantile Regression for the 25 th Percentile	PP
14.2.1.10.3	Supportive Analysis: eGFR Slope Analysis Using Quantile Regression for the 75 th Percentile	ITT
14.2.1.10.4	Supportive Analysis: eGFR Slope Analysis Using Quantile Regression for the 75 th Percentile	PP
14.2.1.11	Sensitivity Analysis Due to Elevated Serum Creatinine: eGFR Slope Analysis Using Quantile Regression	ITT
14.2.1.12.1	eGFR Slope Analysis Using Quantile Regression for the Median by Gender	ITT
14.2.1.12.2	eGFR Slope Analysis Using Quantile Regression for the Median by ADA Status	ITT
14.2.1.12.3	eGFR Slope Analysis Using Quantile Regression for the Median by FD Classification	ITT
14.2.1.12.4	eGFR Slope Analysis Using Quantile Regression for the Median by eGFR	ITT
14.2.1.12.5	eGFR Slope Analysis Using Quantile Regression for the Median by eGFR Slope	ITT
14.2.1.12.6	eGFR Slope Analysis Using Quantile Regression for the Median by Usage of ACEi or ARB	ITT
14.2.1.12.7	eGFR Slope Analysis Using Quantile Regression for the Median by Region	ITT
14.2.1.12.8	eGFR Slope Analysis Using Quantile Regression for the Median by UPCR Categories	ITT
14.2.2.1	Kidney Function - Proportion of Patients who Achieve Therapeutic Goals	ITT
14.2.2.1.1	Kidney Function - Proportion of Patients who Achieve Therapeutic Goals by Gender	ITT
14.2.2.1.2	Kidney Function - Proportion of Patients who Achieve Therapeutic Goals by ADA Status	ITT

	Kidney Function - Proportion of Patients who Achieve	
14.2.2.1.3	Therapeutic Goals by FD Classification	ITT
	Kidney Function - Proportion of Patients who Achieve	ITT
14.2.2.1.4	Therapeutic Goals by UPCR Categories	
	Kidney Function Therapeutic Goals - Shift Table from Baseline to	
14.2.2.2	Post-treatment	ITT
44222	Kidney Function Therapeutic Goals - Shift Table from Baseline to	20
14.2.2.3	Post-treatment	PP
14.2.3.1	Summary of Plasma Lyso-Gb3 Concentrations	ITT
14.2.3.1.1	Summary of Plasma Lyso-Gb3 Concentrations by Gender	ITT
14.2.3.1.2	Summary of Plasma Lyso-Gb3 Concentrations by ADA Status	ITT
14.2.3.2	Plasma Lyso-Gb3 Change from Baseline - MMRM	ITT
14.2.3.2.1	Plasma Lyso-Gb3 Change from Baseline – MMRM by Gender	ITT
44222	Plasma Lyso-Gb3 Change from Baseline – MMRM by ADA	1
14.2.3.2.2	Status	ITT
44000	Plasma Lyso-Gb3 Change from Baseline – MMRM by FD	
14.2.3.2.3	Classification	ITT
44222	Proportion of Patients whose Plasma Lyso-GB3 Improved for	ITT
14.2.3.3	Different Cutoffs	ITT
442224	Proportion of Patients whose Plasma Lyso-GB3 Improved for	177
14.2.3.3.1	Different Cutoffs by Gender	ITT
14.2.3.3.2	Proportion of Patients whose Plasma Lyso-GB3 Improved for	ITT
14.2.3.3.2	Different Cutoffs by ADA Status	111
14.2.3.3.3	Proportion of Patients whose Plasma Lyso-GB3 Improved for	ITT
14.2.3.3.3	Different Cutoffs by FD Classification	111
14.2.4.1	Summary of Plasma Gb3 Concentrations	ITT
14.2.4.1.1	Summary of Plasma Gb3 Concentrations by Gender	ITT
14.2.4.1.2	Summary of Plasma Gb3 Concentrations by ADA Status	ITT
14.2.5.1	Summary of Urine Lyso-Gb3 Concentrations	ITT
14.2.5.1.1	Summary of Urine Lyso-Gb3 Concentrations by Gender	ITT
14.2.5.1.2	Summary of Urine Lyso-Gb3 Concentrations by ADA Status	ITT
14.2.6.1	Summary of Cardiac MRI by Hypertrophy Status	ITT
14.2.6.1.1	Summary of Cardiac MRI by Gender and by Hypertrophy Status	ITT
142612	Summary of Cardiac MRI by FD Classification and by	ITT
14.2.6.1.2	Hypertrophy Status	ITT
14.2.6.2	Cardiac MRI - Shift in LVMI Fibrosis Segments	ITT
14.2.6.3	Cardiac MRI – Shift in Hypertrophy Status	ITT
14.2.7	Echocardiogram Qualitative Assessments – Shift from Baseline	ITT
14.2.8.1	Summary of Short Form Brief Pain Inventory - Severity Domains	ITT
142011	Summary of Short Form Brief Pain Inventory - Average Pain	ITT
14.2.8.1.1	Over 24 Hours by Gender	ITT
14.2.8.1.2	Summary of Short Form Brief Pain Inventory - Average Pain	ITT
14.2.0.1.2	Over 24 Hours by ADA Status	111

Г		T
14.2.8.1.3	Summary of Short Form Brief Pain Inventory - Average Pain Over 24 Hours by FD Classification	ITT
14.2.8.2	Short Form Brief Pain Inventory - Proportion of Patients with Improvement or No Change in Average Pain Severity	ITT
14.2.8.3	Summary of Short Form Brief Pain Inventory - Interference Domains	ІТТ
14.2.9.1	Frequency of UPCR Categories	ITT
14.2.9.1.1	Frequency of UPCR Categories by Gender	ITT
14.2.9.1.2	Frequency of UPCR Categories by ADA Status	ITT
14.2.9.1.3	Frequency of UPCR Categories by FD Classification	ITT
14.2.9.1.4	Frequency of UPCR Categories by Usage of ACEi or ARB	ITT
14.2.9.2	UPCR Categories - Shift from Baseline to Week 52 and to Week 104	ITT
14.2.10.1.1	Summary of Stress Test Qualitative Assessments – Overall Impression	ITT
14.2.10.1.2	Summary of Stress Test Qualitative Assessments – Symptoms	ITT
14.2.10.2	Stress Test Overall Impression - Shift from Baseline	ITT
14.2.11.1	Summary of Mainz Severity Score Index (MSSI)	ITT
14.2.11.2	Mainz Severity Score Index (MSSI) Overall Score - Shift from Baseline	ITT
14.2.12.1	Summary of Quality-of-Life EQ-5D-5L Overall Health Score	ITT
14.2.12.2	Frequency of Quality-of-Life EQ-5D-5L Qualitative Assessments	ITT
14.2.12.3	Proportion of Patients with Improvement or No Change of Quality-of-Life EQ-5D-5L Qualitative Assessments	ITT
14.2.13.1	Proportion of Patients Used Pain Medications	ITT
14.2.13.2	Number of Different Pain Medications Used by Patients During the Study	ІТТ
14.2.13.3	Number of Patients with Pain Medication Use – Shift from Baseline to Last Visit	ITT
14.2.14	Proportion of Patients with Fabry Clinical Events	ITT
14.3.1	Summary of Exposure	Safety
14.3.1.1	Summary of Exposure by Gender	Safety
14.3.1.2	Summary of Exposure by ADA Status	Safety
14.3.1.3	Summary of Exposure by FD Classification	Safety
14.3.1.4	Summary of Exposure by eGFR	Safety
14.3.1.5	Summary of Exposure by eGFR Slope	Safety
14.3.1.6	Summary of Exposure by Usage of ACEi or ARB	Safety
14.3.1.7	Summary of Exposure by Region	Safety
14.3.1.8	Summary of Exposure by UPCR Categories	Safety
14.3.2.1	Number of Infusions Overall and by Location of Administration	Safety
14.3.2.2	Summary of Infusion Duration (Hours)	Safety
14.3.3.1	Summary of Treatment Emergent Adverse Events	Safety
14.3.3.1.1	Summary of Treatment Emergent Adverse Events by Gender	Safety

14.3.3.1.2	Summary of Treatment Emergent Adverse Events by ADA Status	Safety
	Summary of Treatment Emergent Adverse Events by FD	•
14.3.3.1.3	Classification	Safety
14.3.3.1.4	Summary of Treatment Emergent Adverse Events by Region	Safety
14.3.3.2	Summary of Injection Site Reaction	Safety
14.3.3.3	TEAE by MedDRA System Organ Class and Preferred Term	Safety
14.3.3.4	TEAE by MedDRA System Organ Class and Preferred Term and by Severity	Safety
14.3.3.5	TEAE by MedDRA System Organ Class and Preferred Term and by Relationship to Study Drug	Safety
14.3.3.6	Serious TEAE by MedDRA System Organ Class and Preferred Term	Safety
14.3.3.7	Serious TEAE by MedDRA System Organ Class and Preferred Term and by Relationship to Study Drug	Safety
14.3.3.8	Summary of IRR–2H by Location of Administration	Safety
14.3.3.8a	Summary of IRR–24H by Location of Administration	Safety
14.3.3.8.1	Summary of IRR–2H by Gender	Safety
14.3.3.8.2	Summary of IRR2H by ADA Status	Safety
14.3.3.8.3	Summary of IRR2H by FD Classification	Safety
14.3.3.8.4	Summary of IRR-2H by Region	Safety
14.3.3.9	IRR-2H by MedDRA System Organ Class and Preferred Term	Safety
14.3.3.9a	IRR-24H by MedDRA System Organ Class and Preferred Term	Safety
14.3.3.10	IRR-2H by MedDRA System Organ Class and Preferred Term and by Severity	Safety
14.3.3.10a	IRR-24H by MedDRA System Organ Class and Preferred Term and by Severity	Safety
14.3.3.11	IRR-2H by MedDRA System Organ Class and Preferred Term and by Seriousness	Safety
14.3.3.11.a	IRR-24H by MedDRA System Organ Class and Preferred Term and by Seriousness	Safety
14.3.4	Vital Signs During the Study and Change from Pre-Dose	Safety
14.3.5	Summary of Physical Examinations	Safety
14.3.6.1	Summary of Hematology Test Results	Safety
14.3.6.2	Summary of Coagulation Profile at Screening	Safety
14.3.6.3	Summary of Vitamin D at Screening	Safety
14.3.6.4	Summary of Urine Analysis Test Results	Safety
14.3.6.5	Summary of Biochemistry Test Results	Safety
14.3.7.1	Summary of Electrocardiography (ECG) Quantitative Parameters	Safety
14.3.7.2	Summary of Electrocardiography (ECG) Qualitative Parameters	Safety
14.3.8.1	Summary of Anti-Drug Antibodies	Safety
14.3.8.2	Anti-Drug Antibody Shift from Baseline	Safety
14.3.8.2a	Anti-Drug Antibody Shift from Baseline to Week 104	Safety
14.3.9.1	Summary of Concomitant Medications	Safety

14.3.9.2	Proportion of Patients who Used ACEi and/or ARB	Safety
14.3.9.3	Proportion of Patients who Used Infusion Premedication	Safety
14.3.9.4	Number of Patients with Infusion Premedication (Medication Classes) Use - Shift from Baseline	Safety
14.3.9.5	Summary of Infusion Premedication	Safety
14.3.9.6	Infusion Premedication and IRR	Safety

